**Table 3. Dose Groups for Dose-response Model**

Total Monthly Dose	Treatment Arm	Injection Regimen	Number of Participants
0 mg	Placebo	Single or double injection Q2W or Q4W	40
80 mg	80 mg Q4W	Single injection Q4W	20
120 mg	60 mg Q2W, 120 mg Q4W	Single injection Q2W, Double injection Q4W	40
160 mg	80 mg Q2W, 160 mg Q4W	Single injection Q2W, Double injection Q4W	80
240 mg	120 mg Q2W	Double injection Q2W	40
320 mg	160 mg Q2W	Double injection Q2W	40

### 5.2.1.1. Principal Stratum Estimand Approach

A principal stratum estimand approach will be applied to primary and key secondary endpoints as a supplementary analysis. The estimator based on method A and stratum  $S_{*+}$  of [2] will be used to estimate the difference of treatment effect between each dose of vupanorsen and placebo. It aims to compare the average endpoint response in those who adhere to vupanorsen, with their virtual twin endpoint response that would have been observed on placebo [2]. More specifically, for subjects who are able to adhere to their randomized vupanorsen group (reference FASps), their “hypothetical” expected percent change from baseline at Week 24 in the placebo group will be derived using a 2-step regression approach. In terms of treatment adherence, subjects adhere to the treatment if they are on-treatment until Week 24 with no initiation of treatment of hypertriglyceridemia. This two-step approach has an underlying assumption that the endpoint is normally distributed conditional on baseline value and all intermediate post-baseline measurements (ie, post-baseline visits prior to Week 24) and is implemented as follows. First a linear regression will be constructed by regressing the endpoint of interest on baseline value and intermediate post-baseline measurements, restricted to all FAS subjects in the placebo group (ie, regardless of treatment adherence, reference FASps). Next, linear regressions characterizing linear relationships between each of the intermediate post-baseline measurements and baseline value will be estimated, still using the same placebo dataset. By combining these two steps of linear regressions and use of subjects’ baseline values as input, their “hypothetical” value in the placebo group can be estimated. Then the average difference between subjects’ actual value of percent change from baseline at Week 24 and their corresponding “hypothetical” expected value in the placebo group will be calculated as the estimate of difference of treatment effect for each dose of vupanorsen groups. Bootstrap, a non-parametric statistical method will be used to estimate the variance of the difference of treatment effect, and at least 5000 bootstrap samples will be generated for the estimation of variance, 95% CI and empirical p-value (ie, proportion of bootstrap samples with estimates as extreme as or more extreme than the observed).

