#### 4.4. Other Analysis Sets

FAS\_ps will be the analysis set for supplementary analyses using the principal stratum estimand (Section 2.1.3.2). The set is defined differently in vupanorsen groups vs placebo group. For vupanorsen groups, this set consists of FAS subjects who adhere to the randomized treatment group with no occurrence of intercurrent events. In other words, subjects who prematurely discontinue treatment or are assigned additional medication for treatment of severe hypertriglyceridemia prior to Week 24 will be excluded from this set. However, for the placebo group, the set is simply the FAS restricted to the placebo group, regardless of treatment adherence.

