#### 5.1. Hypotheses and Decision Rules

The null hypothesis for the primary endpoint is:

$H_0$ : There is no difference in mean percent change from baseline in non-HDL-C at Week 24 between vupanorsen and placebo.

The study objective is treatment effect estimation and dose selection and therefore no formal decision rules for inferential purposes are planned. Each vupanorsen treatment group will be compared to the pooled placebo group, ie, placebo-adjusted LS-mean treatment effect for each dose will be reported along with 95% CI and p-value without adjustment for multiple comparisons to placebo.

The Mixed Model Repeated Measurements (MMRM) will be used as the primary statistical method to estimate the difference of treatment effect between each dose of vupanorsen versus placebo at Week 24. Statistical inference including effect size, p-value, 95% CI will be presented for primary and secondary endpoints respectively, with no adjustment for multiplicity.

Although an interim analysis will occur at Week 16, no formal hypothesis testing nor statistical inference will be conducted.

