In addition to the primary analysis, the following three supplementary analyses will be conducted for additional evaluation of the primary and key secondary endpoints (ie, evaluated at Week 24). The first two, one using the MMRM model and the other using the multiple imputation using retrieved dropouts (MI-RD) approach, based on the TP estimand will be applied to the FAS (ie, including data collected post occurrence of intercurrent events as defined in [Section 2.1.3.1](#)). The last one, will be conducted in the framework of the principal stratum estimand, with details to be described in [Section 5.2.1.1](#). One sensitivity missing data analysis ([Section 5.3](#)) under the assumption of missing not at random (MNAR) will be implemented to evaluate the robustness of the primary results, for primary and key secondary endpoints. As in the primary analysis, both supplementary and sensitivity analyses will report the estimates for treatment arms.

Apart from the above statistical efficacy analyses, a Bayesian dose-response model will be constructed to model the relationship between percent change from baseline at Week 24 and doses listed in [Table 3](#), along with estimated 95% CI, for each of the primary and selected key secondary endpoints ([Appendix 1](#)) respectively. The parameter estimates from the phase 2a study will inform the model estimation, ie, used as prior distribution of the 3 parameters (E0, Emax, ED50) and the standard deviation of the residual term.

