## Sensitivity Analyses

To assess the robustness of the primary analysis, the RTB analysis based on the primary estimand but an assumption of MNAR will be conducted ([Section 5.3](#)), using the FAS analysis set.

For each supplementary/sensitivity analysis, the least-squares (LS) means, the 95% confidence interval for the LS means, the difference in the LS means between each dose of vupanorsen and placebo, its corresponding 95% confidence interval and p-value will be presented.

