##### **6.2.1.2. Sensitivity/Supplementary Analysis**

Same as primary endpoint ([Section 6.1.1.2](#)).

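### The principal-stratum bootstrap p-value has no null reference: as written it stays near 0.5 or above, even when the 95% CI excludes zero

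*SAP*

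**What the plan says.** SAP Section 5.2.1.1 predicts, for each participant who adheres to vupanorsen, the Week 24 value expected on placebo, and averages the observed-minus-predicted differences. Uncertainty comes from a non-parametric bootstrap: "at least 5000 bootstrap samples will be generated for the estimation of variance, 95% CI and empirical p-value". The p-value is then spelled out: "empirical p-value (ie, proportion of bootstrap samples with estimates as extreme as or more extreme than the observed".

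The null hypothesis is stated separately, in SAP Section 5.1: "There is no difference in mean percent change from baseline in non-HDL-C at Week 24 between vupanorsen and placebo". Nothing in Section 5.2.1.1 refers to it. The section does not resample under the null, re-centre the resamples on zero or count resamples beyond zero. It also leaves open whether the p-value is one- or two-sided and which type of bootstrap interval is meant. The example code in SAP Appendix 4 covers only the MMRM and the Bayesian dose-response model.

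Reporting is required. For every supplementary and sensitivity analysis, SAP Section 6.1.1.2 asks that "the difference in the LS means between each dose of vupanorsen and placebo, its corresponding 95% confidence interval and p-value will be presented". Section 6.2.1.2 extends this to the Week 24 secondary endpoints with "Same as primary endpoint". Section 5.1 also says that "no formal decision rules for inferential purposes are planned".

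**The concern.** A p-value measures how unusual the observed estimate would be if the true difference were zero, so its reference distribution must be centred on zero. The resamples that supply a variance and a CI are drawn from the data as observed, and their estimates centre on the observed estimate. Asking what share of them is at least as extreme as that estimate compares the estimate with itself.

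Appendix 1 lists this analysis for five Week 24 endpoints (non-HDL-C, TG, ApoB, LDL-C and ANGPTL3). With seven vupanorsen arms that makes 5 × 7 = 35 reported p-values. Programmed as written, each would be uninformative. Many could sit at about 0.50 beside a 95% CI that excludes zero, in an analysis meant to support the primary result. A programmer who notices must choose a repair that the SAP does not specify.

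**Working it through.** **Inputs.** SD 17.5, 15% treatment discontinuation, two-sided alpha 0.05 and a difference of −20 come from protocol Section 9.2. Arm sizes of 20 and 40 come from SAP Table 1 and give 20 × 0.85 = 17 and 40 × 0.85 = 34 adherers. Placebo stays at 40 because, under SAP Section 4.4, "for the placebo group, the set is simply the FAS restricted to the placebo group, regardless of treatment adherence".

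**The plan's own figure.** With 17 per arm, SE = 17.5 × √(2/17) = 6.00. The half-width is 1.96 × 6.00 = 11.76, and power is Φ(20/6.00 − 1.96) = 91.5%. Both match protocol Section 9.2. The SAP gives no numerical value for the bootstrap p-value.

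**What the definition yields.** Let T be the observed estimate, T* a bootstrap estimate with T* ~ N(T, SE²) approximately, and z = T/SE.

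- Same-direction reading (T < 0): P(T* ≤ T) = 0.5.
- Absolute-value reading: P(|T*| ≥ |T|) = 0.5 + Φ(−2|z|). This is 1.0, 0.66, 0.52 and 0.50 at |z| = 0, 0.5, 1 and 1.96.

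With the plan's SE of 6.00:

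| Estimate | \|z\| | As written, absolute | As written, same direction | Wald p = 2Φ(−\|z\|) |
|---|---|---|---|---|
| 0 | 0 | 1.000 | 0.50 | 1.00 |
| −5 | 0.83 | 0.548 | 0.50 | 0.40 |
| −8 | 1.33 | 0.504 | 0.50 | 0.18 |
| −11.76 | 1.96 | 0.500 | 0.50 | 0.05 |
| −20 | 3.33 | 0.500 | 0.50 | 0.0009 |
| −35 | 5.83 | 0.500 | 0.50 | 5.5 × 10⁻⁹ |

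**Main simulation.** There were 16 scenarios of 400 trials (6400 in all), with 5000 resamples per trial drawn separately by arm: 40 placebo against 17 or 34 adherers, true effect 0, −10, −20 or −35. Assumptions not in the documents: a standardised slope on baseline of −0.12, and errors that are normal or log-normal (log-scale SD 0.6) rescaled to SD 17.5. With complete placebo data the two-step estimator equals a simple regression of Week 24 on baseline (largest difference 2.8 × 10⁻¹⁴ in 200 data sets), so that form was used.

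- Same direction: scenario means 0.495 to 0.507.
- Absolute value: means 0.633 to 0.657 at effect 0, 0.511 to 0.532 at −10, 0.500 to 0.510 at −20 and 0.499 to 0.504 at −35.
- Lowest value in any trial under either reading: 0.420.
- Percentile 95% CI excluding zero at −20: 97.3% (n = 17) and 99.3% (n = 34) with normal errors, 90.2% and 99.0% with skewed errors. At effect 0: 4.8% to 6.5%.

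**With missing placebo data.** The full two-step code was run with 6 of 40 placebo Week 24 values missing at random and five intermediate visits (assumed correlation 0.6), for 48 trials at effects 0 and −20. Same-direction means were 0.498 to 0.501 and the lowest p was 0.463.

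**One trial in full** (40 against 34, true effect −20). The estimate is −18.1 and the percentile CI −27.5 to −9.1. The p-value as written is 0.498 under both readings. Measured against zero, no resample crosses zero (p < 0.0004), the re-centred p is 0.0002 and the Wald p is 0.0001.

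**Second simulation, coded separately.** This used 17 adherers against 34 placebo, six scenarios of 120 trials and 500 resamples per trial. The absolute-value p ranged from 0.42 to 1.00. With normal errors and true effects of 0, −10, −20 and −35, a re-centred p fell below 0.05 in 5%, 46%, 97.5% and 100% of trials, and the percentile CI excluded zero in 3%, 44%, 96% and 100%.

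**The case against.** The best defence is that the parenthesis is a shortened textbook definition in which the null is understood. A p-value is by nature computed under a null, and Section 5.1 supplies one. On that view the text only lacks two words. Literal output would also be conspicuous, since nearly every value would sit near 0.5 or above, so it would probably be caught. The error pushes towards non-significance and cannot manufacture a claim of benefit. The study is exploratory and aimed at estimation, and the interval carries the information that matters.

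Much of this stands as a limit on the consequences. It does not rescue the definition. The implied-null reading needs resamples generated under the null, whereas the SAP uses the same resamples for the CI. Making it work requires an added step, and several are available (re-centring, doubling the smaller tail, a Wald test). They can give different values in small or skewed samples, and the SAP chooses none. Protocol Section 9.2 uses a two-sided alpha, which makes the absolute-value reading more natural, but that reading has the same floor of about 0.5. It is also fair to say that the algebra alone settles the point. The simulations only confirm that finite resampling, skewness and small arms do not change it.

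**Conclusion.** The concern holds. Followed as written, the p-value is about 0.5 under one reading and 0.5 + Φ(−2|z|) under the other, and it does not measure evidence against no difference. The result rests only on ordinary resamples centring approximately on the observed estimate; the assumed slope, error shape and visit correlation do not drive it.

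It affects 35 supplementary p-values. The primary MMRM, the two treatment-policy analyses, the return-to-baseline analysis and the Emax model do not use this p-value. The bootstrap estimate and variance are unaffected by this defect; whether they, or the interval, are adequate in other respects was not tested. The definition should be corrected before programming, but no conclusion of the trial depends on it.

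**What to change.** In SAP Section 5.2.1.1, name the CI type and replace the p-value definition with a two-sided one against zero that matches it. A simple choice is a percentile 95% CI with p = 2 × min(share of bootstrap estimates ≥ 0, share ≤ 0), capped at 1. When the smaller count is zero, report p as below 2/5000 = 0.0004 (with 5000 resamples).

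Two alternatives would also serve:

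- A normal-theory CI with a Wald p-value, both from the bootstrap SE.
- The share of resamples with |T* − T| ≥ |T|, paired with an interval centred on the estimate whose half-width is the 95th percentile of |T* − T|.

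The cost is one or two sentences. The same resamples serve, no further computing is needed, and no other analysis changes.

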### 5.2.2. Analyses for Categorical Endpoints

Categorical endpoints will be summarized using total number of subjects, number of subjects in each response category and percentage, by treatment groups and visits.

Selected binary endpoints, such as post-hoc or pre-specified exploratory lipid or pharmacodynamic endpoints will be analyzed using logistic regression based on MMRM multiple imputation. The missing data at the analysis time point will be first imputed using a normal distribution with the predicted value and variance estimated from the MMRM as the mean, and the variance. A total of 100 imputations will be performed, with each dataset analyzed using a logistic regression adjusting for treatment (categorical) and baseline value (continuous). All 100 results will then be combined into a single estimate using Rubin's rules [3].

### 5.3. Methods to Manage Missing Data

The missing data of the primary hypothetical estimand are defined as all visits post occurrence of intercurrent events (Section 2.1.1). In the primary analysis, due to its inherent assumption of missing at random (MAR), no explicit imputation is needed. The following return to baseline (RTB) sensitivity analysis will be conducted to further evaluate the robustness of the primary results, by using a specific MNAR assumption to impute the missing data of Week 24. Then we will introduce the MI-RD supplementary analysis, as it's the only approach that explicitly imputes missing data, out of all three supplementary analyses.

The RTB missing data sensitivity analysis will be implemented on the same analysis set and hypothetical estimand as the primary analysis, but with a varied assumption, to assess how robust the primary results are. The RTB approach assumes for subjects with missing values at Week 24, their values at Week 24 should eventually return to around their baseline level, ie, their values at Week 24 will be imputed using a normal distribution with the baseline level as the mean and the mean squared error (MSE) from ANCOVA model excluding subjects with missing Week 24 values as the variance. A total of 100 imputations will be performed and each dataset will be analyzed using ANCOVA adjusting for baseline value and treatment group (categorical), then all 100 results will be combined into a single estimate following Rubin's rules [3].

The MI-RD approach serves as additional evaluation of the primary results, along with the other two supplementary analyses. It defines missing data differently, due to the TP estimand it represents. More specifically, it includes data collected post occurrence of intercurrent events in the analysis, and therefore its missing data scope is smaller than the hypothetical estimand. This approach assumes subjects who discontinue the study are expected to have similar values of endpoints, compared to those in the same treatment group that agree to stay in the study for safety follow-up after treatment discontinuation ("retrieved dropouts"), after adjusting for values of baseline visit and last on-treatment visits. The imputation is implemented within groups defined by treatment groups. The missing values at Week 24 are imputed with baseline, last on-treatment visit as predictors, using a regression-based MI approach. The imputation dataset only contains

subjects with missing values of Week 24, together with retrieved dropouts. After a total of 100 datasets are imputed, each completed dataset consisting of all subjects will be analyzed using ANCOVA adjusting for baseline, treatment group. Then all 100 results will be combined into a single estimate [3]. Note if this method is not fully applicable, eg, no sufficient RDs to impute the missing values in one treatment group, then this supplementary analysis might not be produced.

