- m. For WOCBP. Perform serum pregnancy test at Screening. Perform urine pregnancy test prior to dosing at visits on Week 0, Week 2 through Week 24, Follow-up, and Early Termination/Discontinuation (if applicable).
- n. PK sample collected with participants in a fasted state ([Section 5.3.2](#)) at trough (prior to dosing with study intervention) and 2 to 4 hours after administration.
- o. Do not perform assessment/procedure at Day 169 for participants who continued scheduled visits after stopping study intervention and completed Early Termination/Discontinuation assessments/procedures.
- p. ADA samples to be collected prior to dosing with study intervention.
- q. If not collected on the designated collection day, collect at the next available time point when biospecimens are being collected in conjunction with a participant visit.
- r. Assessment to be performed, following ≥4-hour fast, at site (as part of site visit) or separate visit(s) to Imaging facility (see [Section 5.3.2](#)).
- s. Attempts to be made to stay within ±2-hour window of the time when MRI-PDFF was performed at Screening.
- t. Dispense study intervention only to participants assigned to Q2W regimen for home dosing.
- u. For each site visit, perform all indicated procedures and assessments prior to participant self-injection (or caregiver administering injection).
- v. Dosing at home for participants in the Q2W regimens will occur on Weeks 10, 14, 18, and 22; the window for each scheduled dosing day is ±2 days. Study intervention will be dispensed at the prior visit for these doses.

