## **8. STUDY ASSESSMENTS AND PROCEDURES**

The investigator (or an appropriate delegate at the investigator site) must obtain a signed and dated ICD before performing any study-specific procedures.

Study procedures and their timing are summarized in the [SoA](#). Protocol waivers or exemptions are not allowed.

Safety issues should be discussed with the sponsor immediately upon occurrence or awareness to determine whether the participant should continue or discontinue study intervention.

Adherence to the study design requirements, including those specified in the [SoA](#), is essential and required for study conduct.

All screening evaluations must be completed and reviewed to confirm that potential participants meet all eligibility criteria. The investigator will maintain a screening log to record details of all participants screened and to confirm eligibility or record reasons for screening failure, as applicable.

Every effort should be made to ensure that protocol-required tests and procedures are completed as described. However, it is anticipated that from time to time there may be circumstances outside the control of the investigator that may make it unfeasible to perform the test. In these cases, the investigator must take all steps necessary to ensure the safety and well-being of the participant. When a protocol-required test cannot be performed, the investigator will document the reason for the missed test and any corrective and preventive actions that he or she has taken to ensure that required processes are adhered to as soon as possible. The study team must be informed of these incidents in a timely manner.

For samples being collected and shipped, detailed collection, processing, storage, and shipment instructions and contact information will be provided to the investigator site prior to initiation of the study.

The total blood sampling volume for individual participants in this study is approximately 250 mL. The actual collection times of blood sampling may change. Additional blood samples may be taken for safety assessments at times specified by Pfizer, provided the total volume taken during the study does not exceed 550 mL during any period of 60 consecutive days.

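### The supplementary MI-RD analysis imputes Week 24 for participants who completed dosing from participants who stopped drug, which attenuates that one estimate

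*SAP*

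**What the plan says.** MI-RD is one of two supplementary analyses under the treatment-policy estimand; the other is an MMRM on the FAS (SAP 5.2.1 and 6.1.1.2). Appendix 1 plans MI-RD for non-HDL-C, TG, ApoB, LDL-C and ANGPTL3 at Week 24. SAP 5.3 specifies it as follows.

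- **Assumption:** "This approach assumes subjects who discontinue the study are expected to have similar values of endpoints, compared to those in the same treatment group" who "agree to stay in the study for safety follow-up after treatment discontinuation".
- **Model:** "The missing values at Week 24 are imputed with baseline, last on-treatment visit as predictors, using a regression-based MI approach".
- **Strata:** "The imputation is implemented within groups defined by treatment groups".
- **Imputation dataset:** it contains only "subjects with missing values of Week 24, together with retrieved dropouts". All participants return at the ANCOVA step, and 100 results are combined.
- **Fallback:** if there are "no sufficient RDs to impute the missing values in one treatment group, then this supplementary analysis might not be produced".

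The Schedule of Activities places the last Q4W dose at Week 20. For the other regimens, footnote v says "Dosing at home for participants in the Q2W regimens will occur on Weeks 10, 14, 18, and 22". No dose is given at Week 24. Protocol 8 accepts that tests will sometimes be missed: "it is anticipated that from time to time there may be circumstances outside the control of the investigator that may make it unfeasible".

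**The concern.** The assumption and the procedure cover different people. The assumption concerns participants who leave the study. The procedure takes in anyone without a Week 24 value, whatever the reason. A participant can take every scheduled dose and still have a missed visit or an unusable sample. Nothing in SAP 5.3 treats that participant separately, and the model has no term for being on or off drug or for time since the last dose.

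Such a participant therefore gets a value predicted from same-arm participants who stopped drug. Conditioning on the last on-treatment value does not repair this. The regression is fitted in people who went off drug after that visit, so its intercept carries their loss of effect. Placebo has no drug effect to lose, so the error falls on the vupanorsen arms, and more heavily on arms with more missed samples. SAP 5.1 gives the aim as effect estimation and dose selection, so an error that differs by arm is unwelcome even in a supporting analysis.

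**Working it through.** **The plan's own figure.** Inputs from Protocol 9.2: SD 17.5, 20 per arm, 15% discontinuation, so 20 × 0.85 = 17 per arm.

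- Half-width: 1.96 × 17.5 × √(2/17) = 11.76, as stated.
- Power for a difference of -20: 91.5%, as stated (normal approximation).

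The plan gives no figure for MI-RD, so 11.76 serves only as a yardstick.

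**Who fits the model.** The dataset holds two kinds of people: those missing Week 24, who have no outcome, and retrieved dropouts, who have one. Only the second kind can inform the regression.

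**Expected attenuation.** Let m be the share of an arm that completed dosing but lacks Week 24, and r the share of the effect that retrieved dropouts keep at Week 24. Then

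attenuation = m × (1 − r) × |on-drug effect|.

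Neither m nor r is in the documents. I assume m = 2%, 5% or 10%, and r = 0 or 0.5. The on-drug effect is -20, the difference used in Protocol 9.2.

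- r = 0: 0.02 × 20 = 0.4; 0.05 × 20 = 1.0; 0.10 × 20 = 2.0 points.
- r = 0.5: 0.2, 0.5 and 1.0 points.
- r = 1 or m = 0: none.

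**Check by simulation.** This used 2,000 per arm, 150 replicates and 15% stopping with half retrieved (the half is assumed). The regression used baseline and last on-treatment value within arm, with a coefficient of 0.6 on the last on-treatment value (assumed).

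| r | m | No missing data | MI-RD as written | Split by treatment status |
|---|---|---|---|---|
| 0 | 2% | -17.0 | -16.6 | -17.0 |
| 0 | 5% | -17.0 | -16.0 | -17.0 |
| 0 | 10% | -17.0 | -15.0 | -17.0 |
| 0.5 | 2% | -18.5 | -18.3 | -18.5 |
| 0.5 | 5% | -18.5 | -18.0 | -18.5 |
| 0.5 | 10% | -18.5 | -17.6 | -18.5 |

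**Larger effect.** A second simulation took -35% (the target in SAP 7.2), 15% stopping, half retrieved, and an effect that decays with a half-life of 3 to 5 weeks. That range is the plasma elimination half-life in Protocol 2.2.4.1, borrowed here for the lipid effect.

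- The mean imputed value for an on-drug participant was -8.7 to -13.7 instead of about -35.
- With 5% of completers lacking Week 24, the attenuation was 0.90 to 1.07 points; with 2%, 0.36 to 0.43.
- At 5%, completers make up 0.85 × 5% = 4.25% of the arm and unretrieved dropouts 15% × 50% = 7.5%. So 4.25/11.75 = 36% of imputed values would belong to people who never stopped drug.
- One such participant in a 20-person arm moves the arm mean by (35 − 13.7)/20 to (35 − 8.7)/20, about 1.1 to 1.3 points.

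The extreme corner of the formula (m = 10%, full loss, -35%) gives 0.10 × 35 = 3.5 points.

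**Donors available.** With 15% stopping and half retrieved, the expected number of retrieved dropouts is 20 × 0.075 = 1.5, or 40 × 0.075 = 3.0, for a regression with three coefficients. The binomial chance of at least four donors is 5.8% in an arm of 20 and 35% in an arm of 40.

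**The case against.** The strongest reply is that this hardly matters. MI-RD is supplementary, SAP 5.1 sets no formal decision rules, and the shift is small beside 11.76. On the donor counts above, the analysis may often not be run: the chance that all eight arms have four donors is about one in a million (0.058³ × 0.353⁵). That figure is only indicative, since arms with nothing missing need no donors. The fallback sentence foresees the problem. All of this stands and limits the weight of the point.

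Existing provisions also shrink the affected group. The Week 24 analysis window is Day 155 to Day 182 (SAP Appendix 2.1). Protocol Appendix 13 allows home-health draws and, failing those, local laboratories. Under the same appendix a participant who refuses blood draws is discontinued from study intervention, so refusal at a telehealth visit is a weak example of an on-drug missing value. These provisions make m smaller but do not make it zero.

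A further objection is that the split needs a treatment status that may be unknown. The Week 22 home dose is checked from the diary at the Week 24 visit, which is the one missed. The split also moves someone who took every dose and then left the study from the SAP's stated assumption to MAR. Both remarks are fair; they call for a classification rule and an explicit statement, and leave the mismatch in place.

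A reader might infer that the treatment-policy result as a whole is biased, or that MI-RD is the only treatment-policy analysis using off-drug values. The documents do not support either. The treatment-policy MMRM also includes observed off-drug data and does not use this donor rule. MI-RD is only the one supplementary analysis that imputes explicitly.

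**Conclusion.** The point holds for MI-RD alone. As written, the procedure reaches participants whom its stated assumption does not cover, and it biases the vupanorsen estimate toward zero whenever retrieved dropouts have lost some effect by Week 24. A size of about 0.2 to 2 points is reasonable. It rests on assumed rates: 2% to 10% of an arm affected and half to full loss of effect at an on-drug effect of -20%. At -35%, with 2% to 5% of completers affected, the result (about 0.4 to 1.1 points) lies in the same range; only the extreme combination of all three assumptions goes well beyond it. The loss of effect off drug is itself an expectation drawn from the elimination half-life, since the documents give no rate of lipid offset.

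The primary MMRM, treatment-policy MMRM, principal stratum, return-to-baseline and dose-response analyses are unaffected. The reason to act is that the error is systematic, avoidable and follows from the literal text that a programmer would implement.

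**What to change.** Amend SAP 5.3 to split missing Week 24 values by treatment status.

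1. **Treatment discontinued before Week 24:** impute from same-arm retrieved dropouts, as now. The imputation dataset becomes participants who discontinued treatment before Week 24 and have no Week 24 value, plus the retrieved dropouts.
2. **Treatment completed or ongoing:** impute under MAR from same-arm on-treatment participants, using baseline and the on-treatment visits. State that this includes anyone who finished dosing and then left the study.
3. **Final-dose status unknown:** classify by the last documented dose.
4. Run the planned ANCOVA and Rubin combination on the completed datasets.

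The cost is a few sentences, one extra imputation step and the classification rule. No new data are needed. In the simulations, the split brought the bias to about zero.
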